Diagnosis of mixed dyslipidemia ($TG \geq 150 \text{ mg / dL}$ and $TC \geq 200 \text{ mg / dL}$), No drug treatment on lipid profile, signing of the consent letter under information.

People with suspected or confirmed pregnancy, lactating or puerperium, $TC \geq 400 \text{ mg / dL}$ were not included, $TG \geq 500 \text{ mg / dL}$, $BMI \geq 39.9 \text{ kg / m}^2$, DM2, Kidney and / or liver disease, Intolerance to bezafibrate or BBR, PAS / DBP $\geq 140 / 90 \text{ mmHg}$, consumption of drugs with known action on lipid profile, glucose metabolism, BP or body weight.

Elimination criteria. The withdrawal of informed consent, loss of follow-up, presence of a serious adverse event, adherence to treatment $<80\%$ were considered as a reason for exclusion, but not so in the final statistical analysis. Presence of any non-inclusion criteria during the intervention.

Variables

Independent variable

Pharmacological intervention:

Administration of 1500 mg of BBR homologated with 400 mg of placebo (calcined magnesia)

Administration of 400 mg of approved bezafibrate with 1500 mg of placebo (calcined magnesia)

Administration of 1500 mg of BBR with 400 mg of bezafibrate

Dependent variables

Primary: lipid profile (TC, TG, LDL-C, HDL-C, VDL)

Secondary: weight, height, BMI, WC, BP, glucose, creatinine and uric acid, as well as tolerability

Control variables

Diet: They were given general nutrition recommendations based on the provisions of the dietary and physical activity recommendations of the National Academy of Medicine of Mexico, as shown in ANNEX document.

Exercise: They were asked to continue with the daily physical activity they already did and not to increase it.

The patients who came voluntarily for clinical evaluation generally had some cardiovascular risk factor such as dyslipidemia, smoking, etc.

Groups, intervention allocation and blinding

Three groups were formed randomly which were integrated in the following way.

The first group of 12 patients with mixed dyslipidemia received O.V. one 500 mg BBR capsule and one 500 mg placebo capsule at breakfast, one 500 mg BBR capsule at lunch, and one BBR capsule and one 500 mg placebo capsule at night.

The second group of 12 patients with mixed dyslipidemia received one 200 mg bezafibrate capsule in the morning and one 500 mg placebo capsule, one 500 mg placebo capsule with food, and one 200 mg bezafibrate capsule and one of 500 mg placebo in the evening.

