The third group of 12 patients with mixed dyslipidemia received 200 mg of Bezafibrate in the morning with 500 mg of BBR, a 500 mg capsule of BBR in the meal and finally a 200 mg capsule of bezafibrate and a 500 mg of BBR at night.

During the visit at the beginning of the intervention period, all participants who met the inclusion criteria and agreed to participate in the study were asked to select a sealed envelope of 36; 12 sachets from group 1, 12 from group 2 and 12 from group 3, which were mixed. At the time of selection, they were all equal with a number corresponding to each intervention group. Once scrambled, they were arranged in a box and the patient took one at random.

The opening of the envelope selected by each participant allowed to know a numerical code that identified the intervention that the participant received. Blinding was guaranteed in which the participant was unaware of the type of

treatment received, as well as the investigator. At the end of the study when the data were completed, the treatment codes were opened for statistical analysis, this without the person in charge of carrying out the statistical analysis knowing the treatment that the participants received. Participants who left the study without having completed the procedures, but who received at least one dose of the intervention, were taken into account for statistical analysis.

Clinical determinations

All the anthropometric and vital signs determinations as well as the procedures for the interrogation of the physical examination and the integration of the corresponding clinical history were carried out using accepted universal methods and in accordance with the General Health Law in its regulations on the presentation of care services medical.

The physical examination as well as the clinical questioning were performed again on all the occasions required within the development of the study or when adverse events were suspected, which were also directly recorded in the attachment diary of each participant.

Age: defined as the number of years elapsed since the patient's date of birth
Gender: considered as the phenotypic sex of the participant at the time of birth and registered as female or male

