The 60 patients who were attended with the intention of knowing whether or not they suffered from mixed dyslipidemia, after carrying out the laboratory procedures, the results showed that 21 patients did not suffer from mixed dyslipidemia, so they did not continue as part of the study, however they were offered nutritional care by nutrition staff. Of the 39 who met the criteria for mixed dyslipidemia, 3 decided not to participate in the study and 36 agreed to participate; They were explained in detail each of the aspects of the project, the consent letter was read and explained under detailed information and they were asked to come the next day or the third day to begin their inclusion in the study and thus have a scheduled visit cycle for each one.

Intervention period

Through the indicated laboratory tests, each of the biochemical selection criteria was identified and documented. The patient who met the inclusion criteria was assigned to one of the intervention groups.

Visit 1. Participants who met the inclusion criteria, signed the consent letter and agreed to participate in the study, were invited to extract one of the sealed envelopes that contained the assignment code to any of the three interventions. A treatment adherence diary was provided to the participant. In the diary, adherence to treatment was recorded day by day and the participant recorded each taking of the intervention, as well as the discomfort that she might feel daily. The indication to take each of the capsules was: "take one capsule from bottle 1 and one from bottle 2 and ingest them with liquid in the first bite of breakfast, one from bottle 3 with the first bite of food and one from bottle 4 and another from jar 5 with the first bite of dinner only Once the first visit was concluded, each patient was asked to come within the next 30 ± 3 days and was asked to keep the attachment diary, as well as the bottles to count the capsules consumed, it is in this visit in which were given the food recommendations that appear in the food guidance guide of the Ministry of Health.⁶³

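### The allocation envelopes carry one code per arm, so decoding one patient's code during the study could unmask all 12 patients in that arm

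*Combined protocol and SAP*

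**What the plan says.** The design is labelled double-blind (Study design). Under Groups, intervention allocation and blinding, the 36 envelopes are made up as "12 sachets from group 1, 12 from group 2 and 12 from group 3, which were mixed", and "they were all equal with a number corresponding to each intervention group". Each patient takes one from a box, and opening it "allowed to know a numerical code that identified the intervention that the participant received". The Visit 1 description (Intervention period) agrees, speaking of "sealed envelopes that contained the assignment code to any of the three interventions".

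On masking, the same allocation section states "Blinding was guaranteed in which the participant was unaware" and says that the investigator was masked too. Codes are to be opened once the data are complete, and the person running the analysis is not to know the treatments.

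The elimination criteria include "presence of a serious adverse event". The documents do not describe a randomisation or kit number specific to a patient, a holder of the code list, or a procedure for opening a single patient's code. The ethics section says patients were identified in the database by initials and a number, but does not link that number to treatment allocation.

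**The concern.** When a code is shared by a whole arm, masking fails by arm and not by patient. Learning what one patient received also decodes every other patient who carries the same number. A serious adverse event is a foreseeable reason to want one patient's treatment known, and the plan gives no way to do that without exposing the arm.

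What is at stake differs by outcome:

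- **Tolerability** (secondary) is the most exposed. It comes from a daily discomfort diary kept by the patient and from adverse-event questioning by staff at the visits.
- **Weight, waist circumference and blood pressure** are measured by project staff, mostly with instruments. **Adherence review** includes physical capsule counts. Both are less exposed.
- **Lipids** (primary) are analysed automatically or calculated from such values, and are little affected.

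**Working it through.** **1. The plan's own numbers.** Inputs from the sample-size paragraphs: SD 35 mg/dL, difference 44.2 mg/dL, Z values 1.96 and 0.842.

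n = 2 × [35 × (1.96 + 0.842) / 44.2]² = 9.85, rounded up to 10 per arm. Adding 20% gives 10 × 1.2 = 12, and 3 × 12 = 36. The plan's 10, 12 and 36 are reproduced, so an arm of 12 is the right unit.

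**2. Level of the code.** The two descriptions of the envelopes agree:

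- Allocation section: one number for each intervention group, and an opened envelope shows a code that stands for the intervention.
- Visit 1: the envelope holds an assignment code to one of three interventions.

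Both describe three codes shared by 12 patients each. The text is an awkward translation, but nothing in it points to 36 different codes.

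**3. One code decoded.** Assume the person who learns the treatment can see the other patients' numbers.

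- Arm-level code: 12 of 36 known (12/36 = 33%), that is, the patient concerned and 11 others. The remaining 24 are narrowed from three possible treatments to two.
- Patient-level code: 1 of 36 known.

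**4. Two codes decoded.** If the two patients are in different arms, the third code follows by elimination and all 36 are known. For two patients picked at random:

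- P(same arm) = 3 × C(12,2) / C(36,2) = 3 × 66 / 630 = 0.314
- P(different arms, all 36 known) = 1 − 0.314 = 0.686
- Expected number unmasked = 0.314 × 12 + 0.686 × 36 = 28.5

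With patient-level codes, two breaks would reveal 2 of 36.

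**5. Effect on the analysis set.** The elimination paragraph says eliminated patients are not excluded from the final analysis, and the allocation section keeps anyone who took at least one dose. A decision to eliminate made by someone unmasked could shorten treatment, but it would not remove the patient from the analysis.

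**The case against.** The strongest reply is that the harm is hypothetical. The codes were to be opened only at the end, and neither a mid-study break nor a serious adverse event is reported. The documents do not say who kept the codes. The bottles are numbered 1 to 5 by dosing slot, with no arm code described on them, so it is an inference that staff could see other patients' numbers. The blinding sentence can also be read as saying only who was masked, without claiming that a break would be contained. All of this stands. It makes the weakness conditional, but it does not supply a patient-level code.

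Four stronger readings are tempting, and the documents do not support them:

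- **Blinding was in fact lost.** Nothing reports this.
- **Staff could guess two thirds of allocations** (12 + 24 × 0.5 = 24 of 36). This needs a break, full enrolment at that time, and codes visible to the person told. None of these is documented as having occurred together. A mere guess at one patient's treatment, if unconfirmed, decodes nothing.
- **Counting used envelopes predicts late allocations.** With no code decoded, counting predicts the number to be drawn and not the treatment. Patients also drew from a mixed box after eligibility and agreement.
- **Unmasked diet advice or elimination biases the lipids.** The diet advice was general guidance given at Visit 1, before a break is likely, and eliminated patients stay in the analysis.

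**Conclusion.** The concern holds as a conditional weakness in the double-blind claim. As described, one decoded code would reveal 12 of 36 treatments and leave 24 with two possibilities, and breaks in two different arms would reveal all 36. Unique codes would limit each break to one patient.

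This rests on two assumptions: that the codes are arm-level, as both descriptions indicate, and that whoever learns a treatment can see other patients' numbers, which is plausible because envelopes were opened at Visit 1 but is not stated. The practical consequence is mainly for tolerability, less for staff-measured secondary outcomes and adherence review, and little for the lipids. No power or type I error figure depends on it. It deserves correction because the remedy costs almost nothing, and it gives no ground for discounting the primary results.

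**What to change.** **If envelopes can still be prepared:** give each envelope and its set of five bottles a unique participant number from 1 to 36. Have someone outside the clinic hold the list linking number to arm, so that a code can be broken for one person only. After data lock, give the analyst a separate A/B/C label that appears nowhere in the clinic. The cost is relabelling 36 envelopes and bottle sets and keeping one list; no patients, visits or assays are added.

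**If the trial is complete,** as the past-tense account of recruitment and the final visit suggests, relabelling is no longer possible and the remedy is reporting. Replace the assurance beginning "Blinding was guaranteed in which the participant was unaware" with a statement that codes were arm-level, who could see them, and whether any code was broken before the data were complete. Interpret tolerability in that light. This costs a few sentences.

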Pérez Rubio et al., 9 conducted a clinical trial in which BBR 500 mg V.O. every 8 h for 12 weeks in a population with metabolic syndrome, reported a significant decrease based on statistical tests in the values of TC (187.0 ± 33.3 vs 175.6 ± 27.0 mg / dL) and TG (215.9 ± 64.7 vs 131.1 ± 51.2 mg / dL), however, HDL-C and LDL-C did not change.

From the group of lipid-lowering drugs, bezafibrate has been a drug of choice for the treatment of hypertriglyceridemia and in combination with some other lipid-lowering drug for the treatment of mixed dyslipidemia.¹⁶

The safety and efficacy of bezafibrate make it a useful drug for the treatment of dyslipidemia, it is well tolerated and can be combined to achieve better control of mixed dyslipidemia. In turn, a meta-analysis of the use of bezafibrate in relation to the lipid profile, showed its effect in reducing the concentration of TC and TG and an increase in HDL-C levels, as well as a cardioprotective effect, which helped in reducing coronary heart disease by up to 28%.¹⁷

A clinical trial where bezafibrate was compared against placebo with a duration of 5 years in which 400 mg of bezafibrate were administered per day, showed a reduction in TG of up to 20.6 mg / dL without showing significant changes on TC, LDL-C, They also report an increase of up to 17 mg / dL of HDL-C.¹⁸

In the Mexican population, another clinical trial was carried out in patients with mixed dyslipidemia, to which bezafibrate was administered at a dose of 400 mg V.O. every 24 h for 12 weeks, it was reported that after treatment and when comparing with baseline values, TG were significantly reduced by 24.4% in the group that was administered bezafibrate (p <0.05), however, the rest of the lipid profile such as CT, HDL-C and LDL-C did not show a significant statistical

difference.¹⁶ This is the first study in which BBR was used in combination with bezafibrate as a therapeutic option for the treatment of mixed dyslipidemia.

HYPOTHESIS

The effect of the administration of the combination of BBR plus bezafibrate modifies the lipid profile in patients with mixed dyslipidemia.

OBJECTIVES

General

To assess the effect of the administration of the combination of BBR plus bezafibrate on the lipid profile in patients with mixed dyslipidemia.

Specific objectives

Determine the concentration of CT, TG, HDL-C, LDL-C, and VLDL-C before and after the intervention with BBR, bezafibrate and BBR plus bezafibrate.

Secondary objectives

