To determine the effect of the administration of BBR, bezafibrate and BBR plus bezafibrate on body weight, height, body mass index (BMI), waist circumference, blood pressure, fasting glucose, creatinine, uric acid.

Describe the tolerability of the administration of BBR, bezafibrate and BBR plus bezafibrate.

METHODOLOGY

To assess the effect of the administration of the combination of BBR plus bezafibrate on the lipid profile in patients with mixed dyslipidemia.

Specific objectives

Determine the concentration of CT, TG, HDL-C, LDL-C, and VLDL-C before and after the intervention with BBR, bezafibrate and BBR plus bezafibrate.

Study design

Single randomized, parallel group, double-blind clinical trial. Resident population of the Guadalajara Metropolitan Area between 30 and 60 years of age, of any sex, with a diagnosis of mixed dyslipidemia.

Study site

Institute of Experimental and Clinical Therapeutics (INTEC) located in the Department of Physiology, University Center for Health Sciences, University of Guadalajara.

The sample size was calculated according to the formula for clinical trials, 61 in which the following values were taken into account for its calculation: The Z_α corresponds to the value of statistical confidence, which was prefixed to a value of $Z_{1-\beta}$ of 95%, for a type I error of 5% expressed as a value of 0.05 with two tails. For this confidence, the value of Z was 1.96.

$Z_{1-\beta}$ that expresses the statistical power or power and was prefixed to the value of $Z-\beta$ of 80%, for a type II error of 20%, which is equivalent to a value of 0.20. For this statistical power and this type II error, the typified Z score was 0.842.

The expression δ refers to the standard deviation in the basal TG concentrations obtained from the BBR studies, which was 35 mg / dL.62 d is the expected TG difference of 44.2 mg / dl.36

The result was $n = 10$ for each intervention group, in order to ensure sufficient statistical power, the sample size was increased by 20% due to possible losses, giving $n = 12$ patients per group.

Inclusion criteria

The study population was selected based on the fulfillment of the following criteria:

Men and women, age completed: 30 to 60 years residents of the Guadalajara metropolitan area, ability to communicate and comply with the established requirements.

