Kruskal-Wallis test to identify differences between the three intervention groups in relation to the quantitative variables of the included participants.

Wilcoxon rank test to identify differences between the baseline and final evaluation of each intervention group in relation to the quantitative variables of the included participants.

Mann-Whitney U test to identify differences between two intervention groups in relation to the quantitative variables of the included participants.

X² test or Fisher's exact test to identify differences between two intervention groups in relation to the qualitative variables of the included participants.

The preset level to consider the probability obtained from any of the statistical methods used was $p \leq 0.05$.

All variables were analyzed with the SPSS v22 program for windows.

Recruitment

15 detection campaigns were carried out in different points of the metropolitan area of Guadalajara, in which 290 people were attended, who were asked if they suffered or were referred to suffer from any cardiovascular disease, dyslipidemia, diabetes, prediabetes, etc. They were determined if they had obesity by calculating the BMI and the WC was determined; A capillary glucose test was also taken, for which a One touch ultra-glucometer was used to discard, by way of scrutiny, any alteration related to glucose metabolism.

Of these patients, 60 reported having a dyslipidemia reference of their own or of a direct relative and were invited to the INTEC located at the University Center for Health Sciences of the University of Guadalajara to carry out a more complete scrutiny.

Scrutiny

Each patient was summoned to INTEC at 08:00 am with a 12-hour fast. The visit during the scrutiny period, like the rest of the scheduled visits, took place at INTEC from 8 a.m. During the first visit, a complete clinical record was integrated, for which a clinical interrogation and comprehensive physical examination were carried out, all the clinical characteristics required for the evaluation of the selection criteria for admission were corroborated. 5 ml of

venous blood were taken by venipuncture with an 18 Gy catheter in the brachial vein to determine the lipid profile (CT, TG, HDL-C) and glucose.

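### The plan does not say which test decides the hypothesis, so a before/after change in the combination arm could settle it without using the randomised comparison

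*Combined protocol and SAP*

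**What the plan says.** The HYPOTHESIS section reads: "The effect of the administration of the combination of BBR plus bezafibrate modifies the lipid profile in patients with mixed dyslipidemia". It names no comparator, and neither does the general objective. The specific objective is to determine five lipid concentrations "before and after the intervention with BBR, bezafibrate and BBR plus bezafibrate", that is, before/after within each arm.

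The METHODOLOGY section calls the study a "Single randomized, parallel group, double-blind clinical trial". The sample-size paragraph uses a two-sided 5% level, 80% power, a triglyceride (TG) SD of 35 mg/dL and an expected TG difference of 44.2 mg/dL. It arrives at 10 per group, raised to 12, and does not say which comparison the 44.2 refers to. Under Variables, five lipids are primary and none is ranked. All three arms receive active drug. Diet advice was given at Visit 1.

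The STATISTIC ANALYSIS PLAN lists:
- Kruskal-Wallis across the three groups.
- Within each arm, "Wilcoxon rank test to identify differences between the baseline and final evaluation of each intervention group".
- Between arms, "Mann-Whitney U test to identify differences between two intervention groups in relation to the quantitative variables of the included participants".

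One threshold, p ≤ 0.05, serves all of them: "The preset level to consider the probability obtained from any of the statistical methods used". No test is called primary, the pair for Mann-Whitney is not named, and the between-arm tests do not say whether they use baseline, day-90 or change values. The Wilcoxon is the only test whose description mentions the final evaluation.

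**The concern.** As worded, the test that fits the hypothesis and the specific objective most directly is the one that makes no use of randomisation. A significant fall in the combination arm would satisfy the hypothesis as written. It would not show that the combination does more than bezafibrate alone or berberine (BBR) alone, because each of those is expected to lower TG by itself. Nor would it separate drug effect from the diet advice or from the passage of 90 days. Treating diet and exercise as control variables limits such influences but does not take them out of a before/after change.

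A second trap follows. With three separate Wilcoxon tests, a result that is significant in the combination arm and not in a single-drug arm is easily read as a difference between arms, which it is not. Only the randomised contrasts remove what the arms have in common.

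**Working it through.** **1. Reproduce the plan's sample size.** Inputs from the sample-size paragraph: z = 1.96 and 0.842, SD 35, difference 44.2.

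- Two-group formula: n = 2 × (1.96 + 0.842)² × 35² / 44.2² = 9.85, so 10 per group. Then 10 × 1.2 = 12, as stated.
- Paired (one-sample) formula with the same inputs: (1.96 + 0.842)² × 35² / 44.2² = 4.92, so 5.

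Only the two-group formula gives the plan's figure. The trial was sized on a between-group TG contrast, and the analysis text ties no test to it.

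**2. What each test would show if BBR added nothing.** The BACKGROUND section reports, for bezafibrate alone, that "after treatment and when comparing with baseline values, TG were significantly reduced by 24.4% in the group that was administered bezafibrate". Give that same 24.4% fall to both the bezafibrate arm and the combination arm, 12 patients each, 20,000 simulated trials per setting, exact two-sided tests at 0.05.

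*(a) Normal data built from BACKGROUND figures.* The baseline and SDs come from the separate BBR trial in metabolic syndrome, "TG (215.9 ± 64.7 vs 131.1 ± 51.2 mg / dL". The 24.4% comes from the bezafibrate trial, so this mixes two populations. Shared fall = 0.244 × 215.9 = 52.7 mg/dL. The baseline–final correlation r is assumed. SD of change = √(64.7² + 51.2² − 2r × 64.7 × 51.2).

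| r | SD of change | Wilcoxon, combination arm | Mann-Whitney on change | Combination significant, single drug not |
|---|---|---|---|---|
| 0.3 | 69.4 | 62% | 5% | 23% |
| 0.5 | 59.1 | 76% | 5% | 18% |
| 0.7 | 46.6 | 92% | 4% | 7% |

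Using that BBR trial's own fall, 215.9 − 131.1 = 84.8 mg/dL, as the shared fall instead, the Wilcoxon rate is about 96–100% and Mann-Whitney stays at 4–5%.

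*(b) Skewed data selected on the entry criteria.* Assumed: lognormal TG with median 205–240 and log-SD 0.45–0.55; within-person CV 15–25%; total cholesterol (TC) mean 232–242, SD 40, within-person CV 6%; TG–TC correlation 0.3. Patients are selected on TG from 150 to below 500 and TC from 200 to below 400. Combination-arm Wilcoxon significant, taking 24.4% as the median fall:
- every patient falls by the same percentage: 66–98%
- response varies between patients, log-SD 0.2: 52–81%
- response varies between patients, log-SD 0.3: 39–58%

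Mann-Whitney on change versus bezafibrate rejects in 4–5% throughout.

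**3. Reading.** Across these settings the Wilcoxon is significant in about 40–98% of trials in which the combination is no better than bezafibrate. The between-arm test keeps to its nominal level. The documents give no effect size for diet or time, so no rate is offered for them.

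**The case against.** The strongest reply is that the plan already contains the right comparison. The trial is randomised and parallel-group, Kruskal-Wallis and Mann-Whitney are listed, and the sample size is a two-group one. The Wilcoxon is a proper answer to the specific objective. No passage claims superiority over either drug; the Introduction says only that the combination could be an alternative. All of this stands, and it narrows the point to a missing decision rule.

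A reader might infer from the simulation that the Wilcoxon has a false-positive rate of 40–98%. That does not follow. In every simulated trial the combination arm truly falls, so these figures are power to detect a real change. They become errors only if the result is taken as evidence of added benefit. A reader might also infer that the sponsor intends to rest its conclusion on within-arm p-values, or that diet would produce a significant fall by itself. The documents support neither: they do not say how the tests will be weighed, and they give no diet effect.

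It is also fair to say that the general objective is not before/after; it merely lacks a comparator. The percentages lean on assumed variability, and the logical point does not depend on them.

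**Conclusion.** The point holds in a limited form. The plan includes valid between-arm tests and was sized for one, but nothing makes them decisive. The comparator-free hypothesis, read with one threshold for all tests, lets a within-arm result confirm it. Such a result can say that lipids changed in the combination arm. It cannot say that the combination caused more change than either component.

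The size of the gap, about 40–98% against 4–5%, assumes a shared 24.4% TG fall, 12 per arm, and the variability and correlation values stated above. Its direction holds in every setting tried. This is a cheap improvement to how conclusions are drawn, not evidence that a wrong conclusion was planned or reached.

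**What to change.** Add to the STATISTIC ANALYSIS PLAN, in substance:

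- Conclusions about the effect of the combination rest on two randomised contrasts, combination versus BBR and combination versus bezafibrate, each by Mann-Whitney on the change in TG from baseline to day 90. TG is chosen because the sample size is based on it.
- A claim that the combination beats each drug alone requires both contrasts at p ≤ 0.05. Otherwise the result is worded by the single contrast won.
- Kruskal-Wallis is the supportive three-group test, and the other four primary lipids are supportive.
- Within-arm Wilcoxon results are descriptive only.
- The choice is disclosed as post hoc. The plan reports the normality result for TG, so its text was written after the data had been inspected. The rule then governs how conclusions are worded and does not control error prospectively.

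Cost: a few sentences and no new data. Before/after p-values no longer support an efficacy claim, and TG is singled out from five primary lipids. Power may also be low. If 44.2 mg/dL is the true gain over a single drug, which the plan does not say, power per contrast at 12 per arm is about Φ(44.2 / (SD × √(2/12)) − 1.96). That is 87% at the plan's SD of 35 and 39% at the 64.7 reported in the BACKGROUND section. Requiring both contrasts lowers it further, to about 75% and 20% by t-test simulation.
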